## 7.3 Pharmacokinetics Analyses

The PK Analysis Set (Section 5.5) will be used for PK analyses.

The PK parameters will be derived for each subject using a non-compartmental approach. The food effect on ASTX029 PK parameters will also be evaluated. Descriptive statistics including mean, standard deviation, median, and range for PK parameters for ASTX029 will be summarized.

Detailed and additional PK analyses are described in a separate PK analysis plan.

## 7.4 Pharmacodynamic Analyses

Assessment of target engagement and biomarker analyses will be performed in blood and tumor tissue biopsies. Secondary endpoint biomarker investigation may include the following:

• Demonstration of target engagement in fresh tumor tissue biopsies (when available) (eg, pRSK and pERK inhibition following ASTX029 treatment).

This analysis of parameters/biomarkers may include descriptive summaries such as mean, standard deviation, median, minimum, and maximum for continuous variables and counts and percentages for categorical variables.

This pharmacodynamic data will be captured as Study Data Tabulation Model (SDTM) data, and listings provided of any analysis that is done.

Exploratory biomarker investigations will include the following:

- Evaluation of cancer cell proliferation and induction of apoptosis in fresh tumor tissue biopsies (when available).
- Suppression of mutant clones in ctDNA.
- Identification of potential biomarkers of ASTX029 activity (DNA, RNA, or protein) in blood and tumor tissue biopsies (archival and fresh biopsies, when available).

The exploratory pharmacodynamic data will not be analysed, listed, or captured as Study Data Tabulation Model (SDTM) data.

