9.2.2. Pharmacodynamic and Biomarker Assessments

Assessment of target engagement and biomarker analyses will be performed in blood and tumor tissue biopsies. Biomarker investigations will include the following:

- Demonstration of target engagement in fresh tumor tissue biopsies (when available) (eg, pRSK and pERK inhibition following ASTX029 treatment).
- Evaluation of cancer cell proliferation and induction of apoptosis in fresh tumor tissue biopsies (when available).
- Suppression of mutant clones in ctDNA.
- Identification of potential biomarkers of ASTX029 activity (DNA, RNA, or protein) in blood and tumor tissue biopsies (archival and fresh biopsies, when available).

Biomarker analyses will be performed by methods including immunohistochemistry, reverse transcription polymerase chain reaction (RT-PCR), next-generation sequencing, and possibly others.

Blood samples will be collected for biomarker analysis at the time points indicated in Table 8. Details of blood sample collection and handling procedures are provided in the laboratory manual.

If a FFPE archived tumor tissue is available, it will be obtained for use in this study during screening. In addition, collection of new (or fresh) tumor biopsies is encouraged (optional) in Phase 1 Part A and Phase 2 and mandatory in Phase 1 Part B of the study at the time points indicated in Table 9.

Archived tissue and fresh biopsies collected at screening will be used to characterize the genetic background of the tumor, confirm mutational status, and identify potential additional biomarkers of response to ASTX029; biopsies collected on treatment will be used to establish target engagement in tumor tissue and changes induced by ASTX029 treatment. At each time point (if safe and feasible), at least 2 biopsy cores will be collected (1 to be fresh-frozen and 1 to be FFPE). The subject must sign a biopsy ICF. A posttreatment biopsy sample need not be collected if a pretreatment biopsy (fresh) is not available for comparison. Details of biopsy tissue collection and handling procedures are provided in the laboratory manual.

Study Day	Dosing Day?	Samples	Time Point
Screening	No	Germline DNA (PBMC), ctDNA	
C1D1	Yes	ctDNA	Predose ^a
C2D1	Yes	ctDNA	Predose ^a
Day 1 of every cycle thereafter	Yes	ctDNA	Predose ^a
Treatment Termination visit	No	ctDNA	

 Table 8:
 Sample Collection Schedule for Biomarker Analyses

CxDx=Cycle x Day x; ctDNA=circulating tumor DNA; PBMC=peripheral blood mononuclear cell.

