11.9. Pharmacodynamic/Biomarker Analyses

The Pharmacodynamic and Biomarker Analyses Set (Section 11.2.5) will be used for pharmacodynamic and biomarker analyses.

Values at baseline and changes from baseline (if appropriate) of the pharmacodynamic parameters and biomarkers assessed in the study will be summarized descriptively using mean, standard deviation, median, minimum, and maximum for continuous variables and counts and

percentages for categorical variables. Summaries will be provided separately for each regimen in Phase 1 Part A, for the RDE cohort(s) in Phase 1 Part B, and for each cohort in Phase 2.

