## 2.3 Exploratory Objectives

To identify and evaluate biomarkers of ASTX029 activity.

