#### 3.2.3 Exploratory Endpoints

- Suppression of mutant clones in circulating tumor DNA (ctDNA).
- Explore additional biomarkers of ASTX029 activity.

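### SAP 7.4 rules out any output for the ctDNA endpoint, contradicting the descriptive summaries promised in Protocol 11.9, and SAP 7.9 does not declare the change

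*SAP*

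**What the plan says.** **The objective and endpoint.** SAP 2.3 has one exploratory objective: "To identify and evaluate biomarkers of ASTX029 activity". SAP 3.2.3 puts two exploratory endpoints under it: suppression of mutant clones in ctDNA, and a general item on further biomarkers of activity.

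**The analysis section.** SAP 7.4 introduces its exploratory list with "Exploratory biomarker investigations will include the following". The list has three items: proliferation and apoptosis in fresh biopsies, ctDNA mutant-clone suppression, and the search for potential biomarkers in blood and tissue. The next sentence reads "The exploratory pharmacodynamic data will not be analysed, listed, or captured as Study Data Tabulation Model (SDTM) data". Earlier in the same section the secondary target-engagement data (such as pRSK and pERK) are handled the opposite way: "This pharmacodynamic data will be captured as Study Data Tabulation Model (SDTM) data, and listings provided of any analysis that is done".

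**The protocol.** Protocol 11.9 says "Values at baseline and changes from baseline (if appropriate) of the pharmacodynamic parameters and biomarkers assessed in the study will be summarized descriptively", and "Summaries will be provided separately for each regimen in Phase 1 Part A, for the RDE cohort(s) in Phase 1 Part B, and for each" Phase 2 cohort. Protocol 9.2.2, Table 8, schedules ctDNA at screening, Cycle 1 Day 1, Cycle 2 Day 1, "Day 1 of every cycle thereafter", and the Treatment Termination visit.

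**Which text governs.** SAP 1.0 says that its analyses replace the higher-level plan in the protocol. It exempts only the analyses in a separate pharmacometrics plan.

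**The concern.** The SAP sets up an endpoint and then withdraws every form of output for it. The withdrawal is a stated rule, not a gap in detail: a programmer who follows SAP 7.4 would produce no ctDNA dataset, listing or table.

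That rule reverses a commitment in the protocol without saying so. The clinical study report would then carry a named endpoint with no planned result, and a reader could not tell whether the analysis was dropped on purpose, moved to another report, or lost in drafting. Meanwhile subjects continue to give the samples on the protocol's schedule.

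**Working it through.** No sample size, power or error rate bears on this point, and the plan gives no figure to reproduce. The check compares the texts and counts the scheduled draws.

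**1. Does the closing sentence of SAP 7.4 cover the whole exploratory objective?** Yes. It refers to the exploratory pharmacodynamic data as a class and directly follows the three-item list. Those three items are everything SAP 7.4 offers towards the objective in SAP 2.3.

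**2. Do the two documents conflict?**

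| Question | Protocol 11.9 | SAP 7.4, exploratory data |
|---|---|---|
| Descriptive summary of baseline and change? | Yes, for the biomarkers assessed | No |
| Split by regimen, RDE cohort or Phase 2 cohort? | Yes | None |
| Listing? | Not addressed | No |
| Captured as SDTM? | Not addressed | No |

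The first two rows contradict each other.

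**3. Does the protocol text rescue the endpoint?** No. SAP 1.0 gives the SAP precedence.

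**4. Is the change declared?** No. SAP 7.9 lists three changes: a relabelled column in the response table, the fact that only Regimen 1 was opened, and the added Enrolled Subject Analysis Set. The removal of the exploratory biomarker analysis is not among them. SAP 5.6 still defines a set for pharmacodynamic and biomarker analyses.

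**5. Does another plan cover it?** None is named. SAP 1.0 exempts a pharmacometrics plan, and SAP 7.3 points to a PK analysis plan. Neither is described as covering ctDNA.

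**6. How much sampling is involved?** From Table 8, for a subject who has the Treatment Termination visit:

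draws = 1 (screening) + number of cycles started + 1 (Treatment Termination)

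- 2 cycles started: 1 + 2 + 1 = 4
- 6 cycles started: 1 + 6 + 1 = 8

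The visit-by-visit text (Protocol 9.4.11.9) carries the predose ctDNA draw through Cycle 6. Protocol 9.4.12 then leaves the later schedule to the investigator and does not include ctDNA in its stated minimum. The extension schedule (Table 13) has no ctDNA. The count is therefore firm only up to Cycle 6.

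Planned SAP tables, listings or SDTM records from these draws: 0.

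**The case against.** The best defence is about scope. SAP 1.0 describes analyses and reporting by the sponsor's biostatistics group, so the closing sentence of 7.4 might only take exploratory data out of that group's package and leave the laboratory work in place. One might also argue that the SDTM phrase qualifies all three verbs, which would make the sentence a remark on data standards. Part of this stands: nothing in the SAP cancels the assays. But the sentence denies analysis and listing as well as capture, directly after the secondary data are granted capture and listings. The SAP also does not say who would report the exploratory results. If only formatting was meant, the sentence still needs correcting.

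Several stronger conclusions are tempting, and the documents do not support them:

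- **That the objective cannot be answered, or that the samples have no planned use.** Protocol 9.2.2 plans laboratory biomarker work, including sequencing. Protocol 7.3 has the DSRC weigh available biomarker data for the RDE and RP2D, although it does not name ctDNA. Protocol 14.2.5 allows later use of stored samples. None of these is a prespecified analysis of the endpoint, but together they limit the claim to the absence of planned statistical output.
- **That sampling is firm in every cycle.** Table 8 read alone says so, but Protocol 9.4.12 makes assessments after Cycle 6 discretionary.
- **That about 900 samples are affected.** Multiplying 3 draws by 300 subjects combines a minimum that applies only to those who reach Cycle 2 with an enrolment ceiling. It also omits the termination draw. The result is neither a floor nor a ceiling, so draws per subject are the safer measure.
- **That an allele-fraction analysis split by tumour response is owed.** Protocol 11.9 promises descriptive summaries by regimen or cohort and no more. A mutant allele fraction may also not apply to the KRAS-amplified tumours allowed in Cohort B or the fusions in Cohort D.

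It is also fair to say that the stakes are low: the endpoint is exploratory, with no hypothesis or decision rule attached.

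**Conclusion.** The point holds as a contradiction between SAP 7.4 and Protocol 11.9 that SAP 7.9 does not declare. Under the governing document, the sole exploratory objective has no planned statistical output, against 4 scheduled ctDNA draws for a subject starting 2 cycles and 8 for one starting 6. This rests on the plain reading of the closing sentence in SAP 7.4 and on neither document naming a biomarker plan. If such a plan exists, the defect shrinks to a missing cross-reference and an undeclared change. The effect is confined to the exploratory objective. ORR, safety and the Simon stage decisions do not depend on it, so this is a desirable correction and not a critical one.

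**What to change.** Replace the closing sentence of SAP 7.4 with text to this effect:

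*ctDNA results will be captured and listed by subject. Values at baseline and changes from baseline will be summarised descriptively by visit, with the number of subjects contributing at each visit, for each regimen in Phase 1 Part A, each RDE cohort in Part B and each Phase 2 cohort, in the set defined in Section 5.6. Where a mutant allele fraction does not apply (KRAS amplification, BRAF fusion), the assay's own measure will be used. Tissue markers with too few samples will be listed only.*

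This restores what Protocol 11.9 already promises. Baseline can follow the general rule in SAP 7.2.

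If the sponsor intends to drop these analyses or report them elsewhere, it should declare that in SAP 7.9, name the document that will report them, and reconcile SAP 2.3, 3.2.3 and 7.4 with Protocol 11.9.

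The first route costs one laboratory data transfer, one listing and one table, assuming that the assays are run; the documents do not give their status. The second costs a few lines of text. Neither changes sampling or any primary or secondary analysis.

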## 7.5 Efficacy Variables and Analyses

Efficacy analyses will be based on the Efficacy Analysis Set (Section 5.3). Efficacy variables will be summarized using descriptive statistics. No comparison between treatment sequences will be performed.

Anti-tumor response is based on Response Evaluation Criteria in Solid Tumors (RECIST) v1.1 (Eisenhauer et al 2009). The details of RECIST v1.1 evaluation of responses can be found in protocol Appendix 3. The principal investigator assessment of RECIST v1.1 response will be analyzed.

Table 1 provides a summary of the overall response status calculation at each time point for subjects who have measurable disease at baseline. Details of complete response (CR), partial response (PR), progressive disease (PD), and stable disease (SD) assessments for Target and Nontarget Lesions are provided in Appendix 3 of the protocol.

Table 1: Summary of Overall Assessment of Response					
Time Point Response: Subjects with Target (±Nontarget) Disease					
Target Lesions	Nontarget Lesions	New Lesions	Overall		

Target Lesions	Nontarget Lesions	New Lesions	Overall Assessment of Response
CR	CR	No	CR
CR	Non-CR/Non-PD	No	PR
CR	Not evaluated	No	PR
PR	Non-PD or not all evaluated	No	PR
SD	Non-PD or not all evaluated	No	SD
Not all evaluated	Non-PD	No	NE
PD	Any	Yes or No	PD
Any	PD	Yes or No	PD
Any	Any	Yes	PD

CR=complete response, NE=inevaluable, PD=progressive disease, PR=partial response; SD=stable disease.

## 7.5.1 Overall Response and Disease Control Rate

The ORR will be calculated as the number of evaluable subjects whose best response is CR or PR, divided by the total number of subjects evaluable for ORR analysis (Section 5.3). The DCR will be calculated as the number of subjects whose best response is CR, PR, or SD, divided by the total number of subjects evaluable for DCR analysis (Section 5.3). The 90% Clopper-Pearson CIs for the ORR and DCR will be provided.

Best response for a subject is defined as the best overall response from all post baseline assessments of a subject in the study. When SD is believed to be the best response, it must also meet the protocol-specified minimum time from baseline (6 weeks). If the minimum time is not met when SD is otherwise the best time point response, the subject's best response depends on the subsequent assessments.

### 7.5.2 Duration of Response

Duration of response will be calculated for all responders from the date of the first documentation of CR or PR to the date of progress or death, whichever occurs first. Duration of SD will be calculated for subjects whose best response is CR, PR, or SD from the day study drug was first taken to the date of disease progression or death, whichever occurs earlier, or the last disease assessment for subjects without disease progression or death.

Duration of response and duration of SD will not be estimated for subjects who leave the study prior to a first assessment of response nor for subjects whose best response is progressive disease.

Duration of response and duration of SD will be analyzed using a K-M method, with the duration being censored at the time of the date of study termination for subjects without a relapse or disease progression. Duration of response and duration of SD will be summarized.

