5.4.4. End of Study

The study will be considered complete (that is, scientific evaluation will be complete [study completion]) following evaluation of safety and efficacy as determined by the Sponsor. Investigators will continue to follow the Schedule of Activities (Table 13) for all patients until notified by the Sponsor that study completion has occurred.

End of the study is the date of the last visit or last scheduled procedure for the last patient.

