11.6.4. Duration of Response

Duration of response will be calculated for all responders from the date of the earliest assessment of CR or PR to the date of relapse or death, whichever occurs earlier, or the last disease assessment date for subjects without a relapse or death. Duration of SD will be calculated for subjects whose best response is CR, PR, or SD from the day study drug was first taken to the date of disease progression or death, whichever occurs earlier, or the last disease assessment for subjects without disease progression or death.

Duration of response and duration of SD will be summarized with descriptive statistics including arithmetic mean, standard deviation, median, and range will be summarized for subjects who have overall responses.

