## 1.0 INTRODUCTION

The purpose of this document is to provide details of the planned analyses for the Phase 1 and 2 ASTX029-01 study. The study is to assess the safety, PK, pharmacodynamics, and preliminary clinical activity of ASTX029 administered orally to subjects ≥18 years of age with advanced solid malignancies who are not candidates for approved or available therapies.

The primary objectives of the Phase 1 portion of this study are to assess safety and to identify the MTD, the RP2D, and the recommended dosing regimen of ASTX029 administered orally. The primary objective of the Phase 2 portion of this study is to assess preliminary clinical activity, as determined by objective response rate (ORR) in tumors characterized by gene aberrations in the MAPK signal pathway that may confer sensitivity to ASTX029.

The analyses specified in this document supersede the high-level analysis plan described in the protocol. Analyses and statistical reporting for ASTX029-01 subjects, with the exception of the analyses that are described in a separate Pharmacometrics Analysis Plan (PAP), will be conducted by Taiho Oncology Biostatistics department using SAS version 9.4 or higher.

This Statistical Analysis Plan (SAP) is based on the ASTX029-01 protocol amendment 5.0 (dated 14 April 2022).

Specifications for data tables, listings and figures are detailed in a separate document.

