## 7.1 Subject Disposition

Subject disposition including number of subjects enrolled, treated, and discontinued from study drug by reason, as well as reasons for withdrawal from study (ie, death, complete consent withdrawal, or lost to follow-up) and subjects ongoing at data-cut will be summarized using frequencies and percentages based on information collected on the study electronic case report form (eCRF). Subjects in the All-Subject Analysis Set (Section Error! Reference source not found.) will be included in the disposition analysis.

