#### 7.5.3 Survival

The OS is defined as the number of days from the day study drug was first taken to the date of death (regardless of cause). Subjects without a documented death date will be censored on the last date they were known to be alive. The OS will be presented using a Kaplan Meier estimate. The 95% CI for median OS will be provided using the Kaplan-Meier method with the log-log transformation. All subjects in the Efficacy Analysis Set (Section 5.3) will be included in the OS analysis. The OS rate at 3, 6, 9 and 12 months (and in subsequent 6-month increments if there are participants still at risk) will be estimated with corresponding two-sided 95% CIs.

Frequency (number and percentage) of participants with death events and censoring reasons will be presented with the overall event and censor rates. The event and censoring reasons are as follows:

- Death
- Ongoing and no death
- Withdrawal of consent
- Lost to follow-up.

The OS time or censoring time and the reasons for censoring will also be presented in a listing

The PFS is defined as the number of days from the start of the study drug to disease progression or death, whichever occurs first. The PFS will be analyzed using a Kaplan-Meier method, with PFS time being censored on the date of the last disease assessment. The 95% CI for median PFS will be provided using the Kaplan-Meier method with the log-log transformation. All subjects in the Efficacy Analysis Set (Section 5.3) will be included in the PFS analysis.

Progression of disease (PD) is included as an overall response in Table 1 above, and combines evaluation target, non-target, and new lesions. Target lesion response of PD is at least a 20% increase in the sum of diameters of target lesions, taking as reference the smallest sum on study (this includes the baseline sum if that is the smallest on study). Non-target lesion response of PD is unequivocal progression of existing nontarget lesions. The appearance of 1 or more new lesions is also considered progression of disease. Additional details can be found in Appendix 3 of the protocol, which is based on RECIST v1.1 (Eisenhauer et al 2009).

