## 7.9 Changes from Protocol

'Overall Response' in Table 13 of the protocol (amendment 5) has been changed to 'Overall Assessment of Response' in Table 1 of this SAP.

The protocol planned for possible Regimen 1 (continuous), Regimen 2 (intermittent), and optional Regimen 3 (intermittent). However, only Regimen 1 (continuous) was opened to enrollment. The analyses in Section Error! Reference source not found. will describe the analysis to be conducted using the data available at completion of Phase 1.

In section 5.2, the Enrolled Subject Analysis Set has been added.

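### SAP 7.5.2 censors duration of response and of stable disease at an undefined study-termination date, contradicting its own text, the PFS rule and the protocol; read as a study-level date, it can only lengthen the estimates

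*SAP*

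**What the plan says.** SAP 7.5.2 defines DOR as running from first documented CR or PR to progression or death, and gives no censoring date in that definition. It defines duration of SD from first dose to progression or death, "or the last disease assessment for subjects without disease progression or death". Its Kaplan-Meier sentence then covers both variables, "with the duration being censored at the time of the date of study termination for subjects without a relapse or disease progression".

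The neighbouring rules are:

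- PFS, SAP 7.5.3: "with PFS time being censored on the date of the last disease assessment". Protocol 11.6.2 has the same rule.
- DOR, protocol 11.6.4: progression or death, "or the last disease assessment date for subjects without a relapse or death".
- Precedence, SAP 1.0: "The analyses specified in this document supersede the high-level analysis plan described in the protocol".
- Declared changes, SAP 7.9: a renamed response table, the regimens actually opened, and "In section 5.2, the Enrolled Subject Analysis Set has been added". The DOR censoring rule is not among them.

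The nearest defined term is in protocol 5.4.4: "End of the study is the date of the last visit or last scheduled procedure for the last patient". SAP 7.1 describes a subject's own exit in different words, "as well as reasons for withdrawal from study (ie, death, complete consent withdrawal, or lost to follow-up) and subjects ongoing at data-cut".

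**The concern.** For duration of SD, one section gives two end dates. For DOR, the study-termination sentence is the SAP's only censoring rule, and it differs from the PFS rule and from the protocol. Because the SAP takes precedence, this rule governs, although nothing marks it as a deliberate change.

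The date can be read as the end of the whole study or as the day a subject leaves it. Responders still ongoing at a data cut have neither date yet, and SAP 6.0 and 7.1 allow for such a cut. The sentence also covers subjects without relapse or progression and leaves out death. Read literally, a responder who dies without progression is both an event and a censored case.

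DOR is a secondary endpoint, and two competent programmers could produce different curves from this section. Under the study-level reading the error runs in one direction only. It can also make a subject's DOR exceed the same subject's PFS, which should not happen. SAP 7.7 leans the same way: it carries subjects lost to follow-up to the data cut-off, whereas protocol 11.11 stops at last contact.

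**Working it through.** The documents state no figure for DOR, so there is none to reproduce. The check compares the rules, establishes the direction, then sizes the effect under stated assumptions.

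**1. Rules side by side, for a subject with no progression or death**

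| Variable | SAP | Protocol |
|---|---|---|
| PFS | last disease assessment (7.5.3) | last disease assessment (11.6.2) |
| Duration of SD | last disease assessment, and also study termination (7.5.2) | last disease assessment (11.6.4) |
| DOR | study termination (7.5.2) | last disease assessment (11.6.4) |

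**2. Direction.** The Kaplan-Meier estimate is S(t) = Π(1 − d/n) over event times up to t. With event times fixed, moving a censoring time later can only keep or enlarge each later n. Each factor therefore stays the same or rises, and S(t) cannot fall.

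**3. One subject (hypothetical).** Response on day 42, last scan on day 126, then lost, study termination on day 700. PFS is censored at 126 days and DOR at 700 − 42 = 658 days.

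**4. Ten responders (hypothetical).** Events at 2, 4, 6, 8, 10 and 12 months; four event-free, with last scans at 1.5, 3, 5 and 7 months; study-level date at 24 months.

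- Last assessment: S(6) = 8/9 × 6/7 × 4/5 = 0.61. S(8) = 0.61 × 2/3 = 0.41, so the median is 8 months. S(12) = 0.
- Study-level: S(6) = 9/10 × 8/9 × 7/8 = 0.70. S(10) = 0.50, so the median is 10 months. S(12) = 0.40.

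**5. Extra time credited.** After Cycle 4, scans are every 4 cycles ± 1 cycle, so 4 × 3 = 12 weeks nominally and at most (4 + 1 + 1) × 3 = 18 weeks. For a subject still on schedule, the gap from last scan to termination is bounded by that. For a lost subject, the credited time can run to the end of a study planned to last 61 months.

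**6. Simulation, 9 responders (29 × an assumed 30% = 8.7), 2,500 runs per setting.** Assumptions:

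- Response at the day-42 or day-84 scan with equal probability, then the protocol scan schedule.
- True progression exponential with median 6 months, dated at the next scan.
- Study termination uniform 9 to 30 months after response.
- 0, 10, 20 or 30% of responders given a loss time: late (uniform 0 to 18 months) or early (exponential, mean 4 months).

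The 12-month event-free rate with last-assessment censoring is about 30%. Change under study-level censoring:

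| Loss timing | Given a loss time | Lost before progression | Change at 12 months | Median unchanged |
|---|---|---|---|---|
| none | 0% | 0% | +0.4 points | |
| late | 10 / 20 / 30% | 5 / 9 / 14% | +2.6 / +4.9 / +7.1 | 89 / 78 / 69% of runs |
| early | 10 / 20 / 30% | 8 / 15 / 23% | +5.4 / +10.3 / +15.2 | 71 / 52 / 36% of runs |

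On the own-exit reading the change is +0.4 to +1.0 points throughout. No run gave a shorter median or a lower 12-month rate under the study-level reading.

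**7. Sensitivity.** Over 18 settings (true median 4, 6 or 9 months; termination 9 to 30 or 4 to 18 months after response; three loss timings), with 0 / 5 / 10 / 20 / 30% actually lost, the 12-month change ranges over 0.3–2.4 / 2.1–5.5 / 3.8–9.1 / 7.5–16.4 / 10.8–23.9 points.

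**8. Large-sample check.** A separate simulation used 40,000 responders, 12-week scans, true median 6 months, a study-level date 6 to 36 months after response, and exponential loss. The 12-month rate is 0.28 under last-assessment censoring at every loss level. Under study-level censoring it is 0.28 / 0.32 / 0.35 / 0.40 / 0.44 / 0.48 with 0 / 10 / 20 / 30 / 40 / 50% lost by 12 months. The median is 8.3 months under both rules up to 30% loss, then 11.0 against 8.3. On the own-exit reading the rate stays at 0.28.

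**The case against.** The study-level reading is not secure. Protocol 5.4.4 is listed as a new section in the protocol's summary of changes. That protocol is dated 23 May 2024, whereas the SAP was approved on 2 April 2024 and says it is based on an Amendment 5.0 dated 14 April 2022. So 5.4.4 is weak evidence of what the SAP meant. The paragraph just before the disputed sentence speaks of subjects leaving the study, which favours the subject's own exit, where the shift is about a point at most. The study-level reading also cannot be applied to responders still ongoing at a cut without a substitute date.

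The 12-month rate is not a planned output for DOR, because SAP 7.5.3 specifies landmark rates for OS only. The median often stays put. Every input that drives the size is assumed. The simulation omits the 3-monthly telephone collection of progression dates (protocol 9.4.15) and the effort to obtain progression data at withdrawal (protocol 5.4.2). Protocol 11.6.4 also sets its end date for a descriptive summary, not for Kaplan-Meier. The definition in SAP 7.5.2 already makes death an event, and the SAP 7.7 point adds little.

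Most of this stands as a limit on size. Because of the telephone follow-up, the loss percentages should be read as responders whose progression is never recorded, not as those who merely stop treatment. None of it supplies a definition, reconciles the two end dates for SD, or explains why DOR and PFS are censored differently. The difficulty at a data cut is a further reason to change the sentence.

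**Conclusion.** The concern holds. The censoring sentence in SAP 7.5.2 conflicts with the SD definition in the same section, with SAP 7.5.3 and with protocol 11.6.4. It rests on an undefined date and governs without being declared as a change. That much follows from the text with high confidence.

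The size is conditional. Under the study-level reading the bias is upward or nil: 0.4 points at 12 months with no loss, and about 3 to 15 points in the main settings with 5 to 23% of responders lost before recorded progression. Under the own-exit reading it is at most about 1 point. These figures assume 9 responders, a 6-month true median, and loss rates and timings that the documents do not give.

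The primary ORR analysis and the Simon decision rule are untouched. This should be fixed before analysis, but it does not threaten the study's main conclusion.

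**What to change.** In SAP 7.5.2, keep the Kaplan-Meier analysis. Censor both DOR and duration of SD at the date of the last disease assessment for subjects with neither progression nor death, as for PFS and in protocol 11.6.4, and state that death is an event for both. If the sponsor does intend another date, it should be defined, justified and listed in SAP 7.9.

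In SAP 7.7, carry subjects lost to follow-up to last contact, as in protocol 11.11. This matters less once 7.5.2 is corrected. The OS and PFS censoring rules in SAP 7.5.3 need no change.

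The cost is two SAP sentences and no new data. Reported DOR may be shorter than under the study-level reading.
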